3.9 Restrictions

The following restrictions apply while the patient is receiving study drug AZD9291 and for the specified times before and after:

1. Female patients of child-bearing potential should use highly reliable methods of contraception from the time of screening until 6 weeks after discontinuing study drug. Acceptable methods of contraception are provided in [Appendix H](#) (Definition of Women of Childbearing Potential and Acceptable Contraceptive Methods).
2. Male patients should be asked to use barrier contraceptives (i.e., by use of condoms) during sex with all partners during the trial and for a washout period of 4 months. Patients should avoid procreation for 4 months after completion of study drug. Patients should refrain from donating sperm from the start of dosing until 4 months after discontinuing study drug
3. Once enrolled, all patients must try to avoid concomitant use of medications, herbal supplements and/or ingestion of foods that are known to be potent inducers of CYP3A4 whenever feasible; but patients may receive any medication that is clinically indicated for treatment of AEs. Such drugs must have been discontinued for an appropriate period before they enter screening and for a period of 3 months after the last dose of AZD9291. All concomitant medications should be captured on the electronic case report form (eCRF). Guidance on medicines to avoid, medications that require close monitoring, and on washout periods is provided (See [Appendix F](#)).
4. If medically feasible, patients taking regular medication, with the exception of strong inducers of CYP3A4, should be maintained on their regular medication throughout the study period. Patients taking concomitant medications whose disposition is dependent upon the Breast Cancer Resistance Protein (BCRP) and/or P-glycoprotein (P-gp) with a narrow therapeutic index should be closely monitored for signs of changed tolerability as a result of increased exposure of the concomitant medication whilst receiving AZD9291. Guidance on medications to avoid, medications that require close monitoring and on washout periods is provided (See [Appendix F](#)).

Patients taking rosuvastatin should have creatine phosphokinase levels monitored (due to BCRP-mediated increase in exposure. If the patient experiences any potentially relevant AEs suggestive of muscle toxicity including unexplained muscle pain, tenderness, or weakness, particularly if accompanied by malaise or fever, rosuvastatin must be stopped and any appropriate further management should be taken.

5. Other anti-cancer therapies including investigational agents, and radiotherapy should not be given while the patient is still on study drug and/or has no disease recurrence

3.10 Discontinuation of investigational product or open-label osimertinib

Patients may be discontinued from IP or open-label osimertinib in the following situations:

- Patient decision. The patient is at any time free to discontinue his/her participation in the study, without prejudice
- Adverse event
- Pregnancy
- Severe non-compliance with the study protocol as judged by the Investigator and/or AstraZeneca representative
- Patients who are incorrectly initiated on IP
- Disease recurrence (for select patients who might have the option of open-label osimertinib upon recurrence, please also see Section 3.3)
- Subsequent progression (for patients who started open-label osimertinib upon recurrence) or until a time when the investigator considers that they are no longer deriving clinical benefit.
- Patients experiencing ILD/pneumonitis, or QTc prolongation with signs/symptoms of serious arrhythmia will not be permitted to restart study treatment.
- Patient completes the treatment period of 3 years (156 weeks) as planned (not applicable to patients receiving open-label osimertinib upon recurrence)

3.10.1 Procedures for discontinuation of a subject from investigational product or open-label osimertinib

At any time, patients are free to discontinue IP without prejudice to further treatment. A patient that decides to discontinue IP will always be asked about the reason(s) for discontinuation of IP and the presence of any AEs. The patient or representative will return all unused study drugs. This will also apply to patients on open-label osimertinib.

As long as the patient does not withdraw consent for the study, visits will be continued according to study plan. Treatment discontinuation visit will be conducted as soon as possible after the patient received the last dose of investigational product and safety follow up will be performed 28 days (+7 days) after drug discontinuation.

“Follow up until disease recurrence” visits should continue according to study plan if the patient discontinues study treatment prior to disease recurrence. Radiological assessments will be performed at 12 weeks, 24 weeks and then every 24 weeks up to 5 years and yearly thereafter (+/- 7 days) (relative to randomisation) until disease recurrence. Serious adverse events considered related to the study procedures must be collected while patients are followed up for disease recurrence.

On discontinuation of randomised study drug, patients will be treated in accordance with the local SoC.

Patients who go onto open-label osimertinib as subsequent therapy will also continue visits according to study plan.

If a patient is withdrawn from study, see Section [3.11](#).

3.11 Criteria for withdrawal from study

At any time, patients are free to withdraw from the study without prejudice to further treatment. A patient who decides to discontinue IP treatment and follow-up assessments will always be asked about the reason(s) and the presence of any AEs. If possible, they will be seen and assessed by an Investigator. Adverse events will be followed up ([See Section 6.3.2](#)); all IPs should be returned by the patient or caretaker.

If patients wish to withdraw their consent to both study drug and study assessments, they should be asked if they are willing to continue with survival follow-up (which can be conducted by telephone). If patients wish to withdraw their consent to further participation in the study entirely, including survival follow-up, this should be clearly documented in the patient notes, “Informed Consent Form addendum – options for withdrawal of consent” and in the clinical study database.

For the OS endpoints, the status of ongoing, withdrawn (from the study), and “lost to follow-up” patients at the time of the primary analysis and final OS analysis, and also at the time of the long-term OS analysis for patients who consent to long-term OS follow-up, should be obtained by the site personnel by checking the patient’s notes, hospital records, contacting the patient’s current physician, and checking publicly available death registries. In the event that the patient has actively withdrawn consent to the processing of their personal data, the vital status of the patient can be obtained by site personnel from publicly available resources where it is possible to do so under applicable local laws.

Withdrawn patients will not be replaced.

3.11.1 Screen failures

Screening failures are patients who do not fulfil the eligibility criteria for the study, and therefore must not be randomised. These patients should have the reason for study withdrawal recorded as ‘Eligibility Criteria not Fulfilled’ (i.e., patient does not meet the required inclusion/exclusion criteria). This reason for study withdrawal is only valid for screen failures (not randomised patients).

3.11.2 Withdrawal of the informed consent

Subjects are free to withdraw from the study at any time (investigational product and assessments), without prejudice to further treatment.

A subject who withdraws consent will always be asked about the reason(s) and the presence of any adverse events (AE). The Investigator will follow up AEs outside of the clinical study. The subject or representative will return unused AZD9291 tablets.

If patients wish to withdraw their consent different option of withdrawal should be discussed and clearly documented in “Informed Consent Form addendum – options for withdrawal consent” and patient notes.

If a subject withdraws from participation in the study, then his/her enrolment/randomisation code cannot be reused.

3.12 Discontinuation of the study

The study may be stopped if, in the judgment of AstraZeneca, study patients are placed at undue risk because of clinically significant findings that:

- Meet individual stopping criteria or are otherwise considered significant.
- Are assessed as causally related to study drug.
- Are not considered to be consistent with continuation of the study.

Regardless of the reason for termination, all data available for the patient at the time of discontinuation of follow-up must be recorded in the eCRF. All reasons for discontinuation of treatment must be documented.

In terminating the study, the Sponsor will ensure that adequate consideration is given to the protection of the patients' interests.

4. STUDY PLAN AND TIMING OF PROCEDURES

Table 1 Study plan up to completion of final DFS analysis

	Screening		Treatment Period					Post-Treatment			
Visit	Part I	Part II ^a	Randomisation	Week 2	Week 4	On treatment	Treatment discontinuation ^b	28 day Follow up ^c	Follow-up until disease recurrence ^d	Follow up for survival	Protocol Section
Timing (timing of each visit to be calculated based on date of randomisation visit)		Day -28 to Day -1	Day 1	Week 2	Week 4	Week 12 then every 12 weeks until 3 years (156 weeks)			Week 12, Week 24 and then every 24 weeks until 5 years (264 weeks) / yearly thereafter	Every 24 weeks until 5 years (264 weeks) / yearly thereafter	
Visit window	N/A	N/A	N/A	+/- 1 day	+/- 3 days	+/- 7 days		+ 7 days	+/- 7 days	+/- 7 days	
Written informed consent for pre - screening	X										4.1.1 10.4
Written main informed consent ^e		X									4.1.1 10.4
Tumour sample ^f	X										4.1.3
Tumour sample at disease recurrence (optional)						X ^g			X ^g		5.7.2
Demographics	X										
Medical/surgical history		X	X								

	Screening		Treatment Period					Post-Treatment			
Visit	Part I	Part II ^a	Randomisation	Week 2	Week 4	On treatment	Treatment discontinuation ^b	28 day Follow up ^c	Follow-up until disease recurrence ^d	Follow up for survival	Protocol Section
Timing (timing of each visit to be calculated based on date of randomisation visit)		Day -28 to Day -1	Day 1	Week 2	Week 4	Week 12 then every 12 weeks until 3 years (156 weeks)			Week 12, Week 24 and then every 24 weeks until 5 years (264 weeks) / yearly thereafter	Every 24 weeks until 5 years (264 weeks) / yearly thereafter	
Visit window	N/A	N/A	N/A	+/- 1 day	+/- 3 days	+/-7 days		+ 7 days	+/-7 days	+/-7 days	
Inclusion/exclusion criteria		X	X								3.1 3.2
Physical examination, height (at screening only), and weight		X	X	X	X	X	X		X		5.2.2
Smoking history		X									
WHO performance status		X	X	X	X	X	X		X		5.3.1
Pregnancy test (WOCBP only)		X	At Investigator's discretion								5.2.1
Ophthalmologic assessment		X	As clinically indicated								5.2.6.1
Vital signs		X	X ^h	X	X	X	X				5.2.5
Clinical Chemistry/Haematology/Urinalysis		X	X ^h	X	X	X	X				5.2.1

	Screening		Treatment Period					Post-Treatment			
Visit	Part I	Part II ^a	Randomisation	Week 2	Week 4	On treatment	Treatment discontinuation ^b	28 day Follow up ^c	Follow-up until disease recurrence ^d	Follow up for survival	Protocol Section
Timing (timing of each visit to be calculated based on date of randomisation visit)		Day -28 to Day -1	Day 1	Week 2	Week 4	Week 12 then every 12 weeks until 3 years (156 weeks)			Week 12, Week 24 and then every 24 weeks until 5 years (264 weeks) / yearly thereafter	Every 24 weeks until 5 years (264 weeks) / yearly thereafter	
Visit window	N/A	N/A	N/A	+/- 1 day	+/- 3 days	+/-7 days		+ 7 days	+/-7 days	+/-7 days	
ECG ⁱ		X	X ^h		X	X	X				5.2.3
Echocardiogram/MUGA (for LVEF)		X				X	X				5.2.4
MRI/contrast CT of brain		X ^j									
CT of Chest and abdomen (including liver and adrenal glands) with contrast for disease control ^k		X ^l				At Week 12, Week 24 and then every 24 weeks relative to randomisation (± 7 days) until 5 years, then yearly until disease recurrence/primary analysis/‘final DFS analysis’					5.1
Other imaging ^m		X	As clinically indicated								5.1
Genetic consent and blood sample (optional) ⁿ		X									5.6

	Screening		Treatment Period					Post-Treatment			
Visit	Part I	Part II ^a	Randomisation	Week 2	Week 4	On treatment	Treatment discontinuation ^b	28 day Follow up ^c	Follow-up until disease recurrence ^d	Follow up for survival	Protocol Section
Timing (timing of each visit to be calculated based on date of randomisation visit)		Day -28 to Day -1	Day 1	Week 2	Week 4	Week 12 then every 12 weeks until 3 years (156 weeks)			Week 12, Week 24 and then every 24 weeks until 5 years (264 weeks) / yearly thereafter	Every 24 weeks until 5 years (264 weeks) / yearly thereafter	
Visit window	N/A	N/A	N/A	+/- 1 day	+/- 3 days	+/-7 days		+ 7 days	+/-7 days	+/-7 days	
Plasma sample for ctDNA and blood borne biomarkers ^e			X (pre dose)			X	X		X		5.7.3
PK blood sample (AZD9291 and metabolites)					X ^p	X ^p					5.4
SF – 36			X (pre dose)			X ^q	X				5.3.4.1
Health Resource Module ^r			X (pre dose)	X	X	X	X				5.3.4.4
Adverse event review					X			X ^s			6
Treatment dispensed/returned			X		X	X					7.7
Concomitant medication					X						7.8

	Screening		Treatment Period					Post-Treatment			
Visit	Part I	Part II ^a	Randomisation	Week 2	Week 4	On treatment	Treatment discontinuation ^b	28 day Follow up ^c	Follow-up until disease recurrence ^d	Follow up for survival	Protocol Section
Timing (timing of each visit to be calculated based on date of randomisation visit)		Day -28 to Day -1	Day 1	Week 2	Week 4	Week 12 then every 12 weeks until 3 years (156 weeks)			Week 12, Week 24 and then every 24 weeks until 5 years (264 weeks) / yearly thereafter	Every 24 weeks until 5 years (264 weeks) / yearly thereafter	
Visit window	N/A	N/A	N/A	+/- 1 day	+/- 3 days	+/-7 days		+ 7 days	+/-7 days	+/-7 days	
Post study treatment discontinuation anti-cancer procedures and treatment								X	X	X	5.3.3
Subsequent response/progression data ^t										X (freq as per SoC)	
Survival Status										X ^u	5.1.3

- a) If screening assessments completed within 14 days they do not need to be repeated on Day 1 if patient's condition has not changed
- b) Treatment discontinuation visit to be performed only for the patients who prematurely discontinued treatment. For the patient who completed 3 years treatment (156 weeks), the last visit (Week 156) in treatment period will be considered as treatment discontinuation.
- c) As a minimum, telephone contact should be made with the patient 28 days (+7 days) following discontinuation of study drug
- d) Follow-up until disease recurrence visits to be performed for the patients who discontinue/completed treatment before disease recurrence
- e) Consent may be taken any time prior to 28 days window; Screening Part II period will start with first study-related assessment
- f) Mandatory: sufficient quantity for central confirmation of EGFR mutation status, retrospective T790M testing and for exploratory analyses
- g) Optional: tumour sample at disease recurrence
- h) Assessments to be completed pre-dose on the visit day

- i) All ECG data (with the exception of screening ECGs) will be collected digitally for the first year, standard ECGs will be performed thereafter; ECG is also to be performed in event of a cardiac AE
- j) MRI or contrast CT of brain must be done before randomisation if not performed prior to surgery. MRI/contrast CT scans of the brain must also be conducted at recurrence.
- k) In the rare case where a patient is intolerant of the contrast medium, the preferred imaging would be CT chest without contrast and MRI abdomen with contrast however non contrast abdominal CT will also be accepted. All recurrences on study need to be confirmed with imaging of the chest and abdomen (including liver and adrenal glands). The imaging method used at baseline (CT or MRI) must be used at each subsequent follow-up assessment. MRI/contrast CT scans of the brain must be conducted at recurrence.
- l) Baseline scans within 28 days of first dose
- m) Required only if suspicious signs/symptoms are not covered by CT of chest and abdomen (including liver and adrenal glands) at baseline and follow-up
- n) If for any reason a sample is not drawn prior to dosing, it may be taken at any visit until the last study visit
- o) Plasma samples 10ml prior to first randomised dose on Day 1; 20-30 ml at every 12 weeks visits. If patient discontinues study treatment prior to disease recurrence, samples should continue to be collected in accordance with the scan schedule until disease recurrence is noted.
- p) Blood sampling at 4 weeks, 24 weeks, 48 weeks, 96 weeks after randomisation. Blood draw to occur 3 times at each visit at following time points: pre-dose, between 0,5 -1,5h post dose, between 2-4 h post dose. 96 week PK sample post IDMC7 analysis will not be collected.
- q) SF 36 at 12 weeks, 24 weeks and then every 24 weeks relative to randomisation (\pm 7 days) until disease recurrence
- r) Patients will be asked about any health resource use between visits (i.e., excluding routine follow-up clinic visits associated with the clinical trial but including both planned and unplanned admissions) at every scheduled visit during the study.
- s) AEs ongoing at treatment discontinuation to be followed through to resolution; thereafter, only SAEs /concomitant medications for SAEs considered related to IP and study procedures to be recorded in eCRF
- t) Investigator assessment of response/progression to be collected
- u) To establish survival status patient will be contacted in the week following date of DCO for IDMC and in the two weeks following date of DCO for primary analysis and subsequent analyses.

Table 2 Study Plan for OS period - post final DFS analysis and up to final OS analysis

	Treatment Period	Post-Treatment			Protocol Section
		Treatment discontinuation ^a	28 day Follow up ^b	Follow up for survival	
Visit	On treatment				
Timing (timing of each visit to be calculated based on date of randomisation visit)	Week 12 then every 12 weeks until 3 years (156 weeks)			Every 24 weeks until 5 years (264 weeks) / yearly thereafter	
Visit window	+/-7 days		+ 7 days	+/-7 days	
Tumour sample at disease recurrence (optional)	X ^c				5.7.2
Physical examination and weight	X	X			5.2.2
WHO performance status	X	X			5.3.1
Pregnancy test (WOCBP only)	At investigator's discretion				5.2.1
Ophthalmologic assessment	As clinically indicated				5.2.6.1
Vital signs	X	X			5.2.5
Clinical Chemistry/Haematology/Urinalysis	X	X			5.2.1
ECG ^d	X	X			5.2.3
Echocardiogram/MUGA (for LVEF)	X	X			5.2.4
Imaging	As per local clinical practice				
Plasma sample for ct DNA and blood borne biomarkers ^e	X	X			5.7.3
Adverse event review ^f	X				6
Treatment dispensed/returned	X				7.7

Visit	Treatment Period		Post-Treatment		Protocol Section
	On treatment	Treatment discontinuation ^a	28 day Follow up ^b	Follow up for survival	
Timing (timing of each visit to be calculated based on date of randomisation visit)	Week 12 then every 12 weeks until 3 years (156 weeks)			Every 24 weeks until 5 years (264 weeks) / yearly thereafter	
Visit window	+/-7 days		+ 7 days	+/-7 days	
Concomitant medication	X				7.8
Post study treatment discontinuation anti-cancer procedures and treatment			X	X	5.3.3
Survival Status				X ^g	5.1.3

- a) Treatment discontinuation visit to be performed only for the patients who prematurely discontinued treatment. For the patient who completed 3 years treatment (156 weeks), the last visit (Week 156) in treatment period will be considered as treatment discontinuation.
- b) As a minimum, telephone contact should be made with the patient 28 days (+7 days) following discontinuation of study drug
- c) Optional: tumour sample at disease recurrence
- d) All ECG data (with the exception of screening ECGs) will be collected digitally for the first year, standard ECGs will be performed thereafter; ECG is also to be performed in event of a cardiac AE
- e) Plasma samples 20-30 ml at every visits
- f) AEs ongoing at treatment discontinuation to be followed through to resolution
- g) To establish survival status patient will be contacted in the week following date of DCO for IDMC and in the two weeks following date of DCO for primary analysis and subsequent analyses.

Table 3 **Study plan for the study extension post final OS analysis and up to long-term OS analysis**

Visit ^a	Follow-up- for survival ^b	Protocol Section
Timing (timing of each visit to be calculated based on date of randomisation visit)	Yearly	1.7, 4.5
Visit window	±30 days	
Survival Status ^c	X	4.3.5

- a) Visits can be conducted by telephone or in person.
- b) Each patient will provide written informed consent to participate in the study extension.
- c) To establish survival status, patient will be contacted on a yearly basis. At the time of analysis, the patient will be contacted for survival status in the 2 weeks following the date of DCO for the long-term OS analysis.

Safety data (all serious or non-serious events of ILD/pneumonitis and cardiac failure, and all SAEs) for patients who are treated with open-label osimertinib will be collected as described in Section 6.3 and Section 6.4.

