4.3.3 Disease recurrence follow-up (up to completion of final DFS analysis)

Patients who complete study treatment prior to disease recurrence or discontinue study drug for reasons other than disease recurrence will be followed up at 12 weeks, 24 weeks and then every 24 weeks up to 5 years (264 weeks) relative to randomisation and yearly thereafter.

In addition to radiological assessments, the following assessments are also required during Disease recurrence Follow up as detailed in the Study Plan ([Table 1](#)).

- Physical examination
- WHO Performance Status
- Plasma samples for ctDNA and blood borne biomarkers
- Serious Adverse event collection (causally related)
- Tumour sample collection at disease recurrence (optional)

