5.3.4.1 SF-36

Patients will be asked to complete a paper based version of the SF-36 v 2 standard ([Appendix G](#)) at the clinic according to the Study Plan ([Table 1](#)). The SF-36 v2 is a validated instrument measuring general health status. The standard version of SF-36 ([Appendix G](#)) has a recall period of four weeks.

The SF-36 v2 consists of 36 items combined into domains, and two aggregated summary scores: MCS (Mental Component Summary) and PCS (Physical Summary Component) ([Ware et al 1993](#)).

The eight domains are Physical Functioning (PF, items 3a-3j), Role-Physical (RP, role limitations caused by physical health problems, items 4a-4d), Bodily Pain (BP, items 7 and 8), General Health (GH, items 1, and 11a-11d), Vitality ((VT, items 9a, 9e, 9g, and 9i), Role-Emotional (RE, role limitations caused by emotional problems, items 5a-5c), Social Functioning (SF, items 6 and 10), and Mental Health (MH, items 9b, 9c, 9d, 9f, and 9h). All of the 36 items (self-reported health transition) are used to score the eight SF-36 domains.

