3.2.8.1. SF-36 v2 (standard)

The SF-36 includes eight domains: Physical Functioning (PF); Role Limitations-Physical (RP), Vitality (VT), General Health Perceptions (GH), Bodily Pain (BP), Social Function (SF), Role Limitations-Emotional (RE), and Mental Health (MH). These can be summarised into two summary scores: The Physical Component Summary (PCS) and Mental Component Summary (MCS). Final scores for each scale range from 0-100 with higher scores indicating better health. The general population has a mean score of 50 with a standard deviation (StdDev) of 10.

The absolute values and change from baseline will be calculated for each domain and summary scale at each scheduled post-baseline assessment. The visit response to the SF-36 at each assessment will also be categorised as improved, worsened and stable based on the

changes from baseline using the criteria for a minimum clinically important difference as shown in Table 3.

Table 3 SF-36 Visit Response Categories

Score	Visit response		
	Improved	Worsened	Stable
PCS	$\geq + 3.1$	$\leq - 3.1$	Otherwise
MCS	$\geq + 3.8$	$\leq - 3.8$	Otherwise
PF	$\geq + 3.5$	$\leq - 3.5$	Otherwise
RP	$\geq + 3.2$	$\leq - 3.2$	Otherwise
BP	$\geq + 4.5$	$\leq - 4.5$	Otherwise
GH	$\geq + 5.7$	$\leq - 5.7$	Otherwise
VT	$\geq + 5.5$	$\leq - 5.5$	Otherwise
SF	$\geq + 5.0$	$\leq - 5.0$	Otherwise
RE	$\geq + 3.8$	$\leq - 3.8$	Otherwise
MH	$\geq + 5.5$	$\leq - 5.5$	Otherwise

Time to deterioration of HRQoL is defined as time from date of randomisation to the date of first clinically important worsening confirmed at the subsequent assessment, or death (by any cause) in the absence of a clinically important worsening, provided death occurs within two assessment visits of the last assessment where HRQoL could be evaluated and regardless of whether the patients withdraws from randomised therapy or receives another anticancer therapy prior to symptom deterioration.

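### Table 1 and its footnote q disagree on whether SF-36 continues after study drug stops, and the SAP's time-to-deterioration endpoint needs those forms

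*Protocol*

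**What the plan says.** Protocol Section 4, Table 1, gives the SF-36 row as "SF – 36 X (pre dose) X ^q X". The three marks fall under randomisation, on treatment and treatment discontinuation. The *Follow-up until disease recurrence* column is empty. Footnote d says who uses that column: "Follow-up until disease recurrence visits to be performed for the patients who discontinue/completed treatment before disease recurrence".

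Footnote q, attached to the on-treatment mark, reads "SF 36 at 12 weeks, 24 weeks and then every 24 weeks relative to randomisation" and gives disease recurrence as the end point. It does not mention the end of treatment.

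For patients who complete three years, "the last visit (Week 156) in treatment period will be considered as treatment discontinuation".

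Protocol 4.3.3 covers the period off drug and before recurrence. It says "In addition to radiological assessments, the following assessments are also required during Disease recurrence Follow up as detailed in the Study Plan" and lists physical examination, performance status, plasma samples, related SAEs and an optional tumour sample. SF-36 is not on the list. Protocol 5.3.4.1 has patients complete the form "at the clinic according to the Study Plan", which leads back to Table 1.

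SAP 3.2.8.1 defines time to deterioration "regardless of whether the patients withdraws from randomised therapy" and requires the first clinically important worsening to be confirmed at the following assessment. SAP 4.3.7.2 makes this, for MCS and PCS, the primary HRQoL outcome. Each score gets half of a two-sided 5% error rate, and the log-rank test is in stage IIA-IIIA. SAP 3.2.8.2 removes a patient from the expected-form count for death, loss to follow-up, study withdrawal or lack of a translation. Stopping drug is not on that list.

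**The concern.** A site working from the table marks or from Section 4.3.3 would stop SF-36 when drug stops. A site working from footnote q would continue every 24 weeks until recurrence. Both could claim to be following the protocol.

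The endpoint is written for the second schedule. It ignores treatment withdrawal, and it needs a second form to turn a worsening into an event. On the first schedule the discontinuation form is the last one, so a worsening that first appears there can never become an event. Nothing is known about quality of life between stopping drug and recurrence, whether the patient stopped early or completed three years. The by-visit mean changes in Protocol 8.5.3 would then also describe mainly patients still on drug.

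**Working it through.** The plan states no number of SF-36 forms, so there is no figure of its own to reproduce. As a check on the visit grid, 12-weekly visits to week 156 give 156/12 = 13, which matches the 13 on-treatment visits in Protocol Table 5.

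**Forms under footnote q (post-baseline, no recurrence)**
- To week 156: weeks 12, 24, 48, 72, 96, 120 and 144 = 7 forms.
- From week 156 to week 264: weeks 168, 192, 216, 240 and 264 = 5 forms.
- Total to week 264: 2 + (264 − 24)/24 = 12 forms.

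**Forms after the discontinuation visit, to week 264**

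For a patient stopping at a scheduled week s of 24 or later, footnote q gives (264 − s)/24.

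| Patient, no recurrence | Table marks | Footnote q |
|---|---|---|
| Stops at week 24 | 0 | (264 − 24)/24 = 10 |
| Stops at week 48 | 0 | (264 − 48)/24 = 9 |
| Stops at week 96 | 0 | (264 − 96)/24 = 7 |
| Completes week 156 | 0 | 5 |

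**What completers could contribute by the data cut-offs**

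SAP 1.3 plans 28 months' recruitment and a cut-off 68-70 months after first randomisation. Weeks = months × 30.4375/7.
- Last patient randomised: 40 to 42 months = 173.9 to 182.6 weeks, so 1 form after week 156 under footnote q (week 168).
- First patient randomised: 68 to 70 months = 295.7 to 304.4 weeks, so 6 forms (weeks 168 to 288, reading the footnote literally as 24-weekly beyond week 264).
- At the 17 January 2020 cut-off, counting from the 26 August 2015 study start in Appendix A: 229.3 weeks, so at most 3 forms (weeks 168, 192 and 216).
- Under the table marks the answer is 0 in every case.

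**Confirmation**

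Week 156 is not on the footnote q grid, which goes from 144 to 168. The end-of-treatment form therefore rests on the discontinuation column alone. A worsening first seen at week 156 would meet its confirming form at week 168 under footnote q. For an early stopper after week 24, the next form comes within 24 weeks. Under the table marks there is no next form.

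**What cannot be computed**

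Patients affected per arm = patients in the tested population × proportion stopping before recurrence × proportion first worse on the discontinuation form. Only the first term is available, approximately: 490/2 = 245 planned per arm in stage II-IIIA. The documents give neither proportion.

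**The case against.** Footnote q hangs only on the on-treatment mark, so it may set on-drug frequency and no more, with recurrence named because recurrence also ends treatment. That reading is possible and removes the conflict in wording. It also makes the gap certain: no off-drug form is then scheduled, while the SAP endpoint still ignores treatment withdrawal. The footnote's timing also matches the recurrence follow-up visits rather than the 12-weekly treatment visits.

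Section 4.3.3 is weaker evidence than it looks. It defers to the Study Plan and is not exhaustive: Table 1 marks subsequent anti-cancer treatment in the same column and 4.3.3 leaves it out. Protocol 3.10.1 continues visits after discontinuation, and the SAP's expected-form rule has no stop at end of drug. These favour footnote q, and sites may well have collected the forms. But a visit can continue without the questionnaire, and the expected-form rule depends on which assessments count as scheduled, which is the open question. The empty cell is unlikely to be a reading error, because the plasma row in the same part of the table keeps its mark in that column.

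By-visit compliance would fall if off-drug forms were expected and not collected. That summary does not separate patients off drug from those on it, so it would not show the cause.

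Two limits stand in full. HRQoL is outside the DFS and OS testing hierarchy, and Protocol 8.5.3 plans only mean changes. And the version history of edition 6.0 says no patients remain on study drug, so correcting Table 1 will recover few forms, if any.

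**Conclusion.** The concern holds as an unresolved conflict between the table marks and footnote q, with Section 4.3.3 in support of the marks. If the marks were followed, there are 0 forms between stopping drug and recurrence, against 5 more to week 264 for a recurrence-free completer or 10 more for a patient stopping at week 24. Worsening first reported at discontinuation is then unconfirmable. All of this is conditional on site practice, which the documents do not describe.

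Three stronger conclusions might be inferred, and the documents do not support them.
- *The affected patients are censored.* SAP 3.2.8.1 and 4.3.7.2 give no rule for an unconfirmed worsening. For missed visits the SAP only points to the SF-36 manual.
- *The loss favours osimertinib because more patients stop it for toxicity.* No stopping rates are given. SF-36 also ends at recurrence on either schedule, so worsening first reported at a recurrence-driven discontinuation is equally unconfirmable. With a DFS hazard ratio of 0.20 in the overall population (Protocol 1.4), those patients would be expected to be mostly on placebo. The net direction is unknown.
- *A specific number of deteriorations is lost.* Any such count needs assumed rates of stopping and worsening. It would also have to be made in stage II-IIIA rather than in all randomised patients, and it would have to allow for patients who recover before a confirming form falls due.

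**What to change.** **Protocol.** Mark SF-36 in the *Follow-up until disease recurrence* column of Table 1 and add it to the Section 4.3.3 list, so that both agree with footnote q for any patient still in that follow-up. State what applies after week 264, where the footnote stays 24-weekly but recurrence visits become yearly.

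**Data already collected.**
- State which schedule sites followed.
- Report by arm, in the stage II-IIIA population used for the test, how many patients lack an off-drug form before recurrence and how many had an unconfirmed worsening at discontinuation.
- State how the SAP treats an unconfirmed worsening, and whether off-drug forms are in the compliance denominator.
- Add a sensitivity analysis of time to deterioration in MCS and PCS that counts worsening on the last available form, with no later form due or received, as an event.

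**Cost.** A table mark and a list entry in the protocol, and one questionnaire at visits already scheduled to week 264 for anyone still in that follow-up. The rest is two counts and one repeat analysis on existing data.
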